receiving the 12 mg BID) or placebo. Patients in Part A, Period 2 will stay on their assigned dose for a maximum of 24 weeks or until they meet the criteria for loss of regrowth maintenance (LOM), defined as an absolute SALT score  $>20$ . Any patient meeting the LOM criteria at any assessment timepoint during Part A, Period 2 will enter Part B of the study and return to their original CTP-543 treatment from Part A, Period 1 (8 mg BID or 12 mg BID). Patients not meeting the LOM criteria (e.g., their absolute SALT score  $\leq 20$ ) at the end of 24 weeks will have the opportunity to continue receiving treatment in the Open-Label Extension study (CP543.5001) or they will complete treatment at Week 24 and return in 4 weeks for the Post-Treatment Safety Follow-up. The study design is depicted in the Study Flow Chart of the Appendix (Section 15.1).

An interim analysis to support regulatory activities related to an upcoming CTP-543 New Drug Application (NDA) submission will be conducted. The focus of the interim analyses will be on safety data and will occur following completion of Part A, Period 1. Additionally, after Part A, Period 1 completion, a PK population analysis will be completed. The PK analysis will be conducted by an outside vendor. This analysis will be described in a separate analysis plan and a separate report will be generated.

The primary efficacy assessment will be conducted when all patients have completed Part A, Period 2. An analysis of safety data will also be conducted. This analysis will be included in the NDA submission as an abbreviated report. Site personnel and patients will remain blinded to individual patient study treatments.

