#### 4. GENERAL ANALYSIS AND REPORTING CONVENTIONS

The following is a list of general analysis and reporting conventions to be applied to this study, unless otherwise specified. Departures from these general policies will be described, if applicable, in the appropriate sections of this SAP. When this situation occurs, the rules set forth in the specific section take precedence over the general policies.

All data displays (tables, listings, and figures) will have a header showing the sponsor company name, protocol number, page number, and display status (i.e. “DRAFT” or “FINAL”), as well as a footer indicating file name and run date/time. Summary tables and data listings will be summarized by treatment group for efficacy and exposure, and by treatment group and overall otherwise. All data for analysis may be listed by-patient.

Specifically, for each Part and Period of the study, the summary table layout will be as follows:

For Part A, Period 1 tables:

Treatment Phase		
CTP-543 8 mg BID	CTP-543 12 mg BID	Total

For Part A, Period 2 tables:

Dose Reduction		Drug Discontinuation		Total
CTP-543 8 mg BID to 4 mg BID	CTP-543 12 mg BID to 8 mg BID	CTP-543 8 mg BID to Placebo	CTP-543 12 mg BID to Placebo	

For Part B tables:

Dose Reduction		Drug Discontinuation		Total
CTP-543 8 mg BID to 4mg BID to 8 mg BID	CTP-543 12 mg BID to 8 mg BID to 12 mg BID	CTP-543 8mg BID to Placebo to 8 mg BID	CTP-543 12 mg BID to Placebo to 12 mg BID	

Note that for all efficacy and exposure tables, the total column will not be displayed.

Categorical variables will be summarized using counts (n) and percentages (%) and will be presented in the form “n (xx.x).” If a count is 0, no percentage will be shown. If a percentage is 100%, 100 will be shown. To ensure completeness, summaries for categorical variables will include all categories, even if no patients had a response in a particular category. Unless otherwise specified, the denominator for each percentage will be based on the number of patients in the population being summarized (header n). Percentages will be rounded to one decimal place.

Continuous variables will be summarized using mean, standard deviation, minimum, maximum, median, and number of patients. The minimum and maximum will be the same precision as the

Concert Pharmaceuticals, Inc.  
Statistical Analysis Plan – CP543.2004

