### **8.2.1. Computation of the Primary Endpoints**

The SALT is a measure of hair loss that quantifies the amount of scalp surface without hair in a pre-specified quadrant of the scalp (right side, top, left side, back), that is further summed after applying a quadrant-specific multiplier indicative of scalp surface area contribution, to provide an overall score of total hair loss. An example of the SALT assessment can be found in Appendix 18.2 of protocol.

The primary endpoints for each Part of the study consist of deriving and categorizing the individual overall SALT scores ( $\leq 20$  versus  $> 20$ ).

Due to the variable time on study for each patient within Part A Period 2, the primary analysis visit will be the End of Part A Period 2, where the last observed non-missing SALT value is selected for each patient. Otherwise, missing data will not be imputed for this descriptive, exploratory study.

Patterns of missing values across visits will be listed and summarized with numbers and percentages by treatment and visit.

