### 9.2. Extent of Exposure

Study drug exposure will be summarized for each treatment group and overall for each Part/Period. The number of days on which study drug was dosed (at least partially), the number of days in the study exposed, and total cumulative dose will be summarized for each treatment group. The number and percentage of patients with at least one drug interruption will also be summarized.

The total number of days in the study exposed will include/ignore drug interruptions. The total number of days on study drug (excluding dose interruptions) and drug compliance will also be summarized, per Section 7.3.

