### 9.3. Adverse Events

An adverse event is any untoward medical occurrence that may appear or worsen in a patient during the course of a study. It may be a new intercurrent illness, a worsening concomitant illness, an injury, or any concomitant impairment of the patient's health, including laboratory test values, regardless of etiology. Any worsening (ie, any clinically significant adverse change in the frequency or intensity of a pre-existing condition) should be considered an adverse event. A diagnosis or syndrome should be recorded on the adverse event page of the eCRF rather than the individual signs or symptoms of the diagnosis or syndrome. A worsening of the condition under study, alopecia areata, will not be reported as an adverse event.

All patients will be monitored for adverse events during the study. Assessments may include monitoring of the following parameters: the patient's clinical symptoms, laboratory, physical examination findings, or findings from other tests and/or procedures.

Adverse events will be coded using MedDRA version 23.1, and summarized by treatment group, system organ class, and preferred term for each Part/Period of the study.

An adverse event reported after informed consent, but before the first dose of study drug (i.e., Day 1), will be considered a pre-treatment adverse event. TEAEs will be defined as any adverse event that occurs after administration of the first dose of study drug in each Part/Period (ie, on or after the day of the first dose in each Part/Period). Adverse events will further be considered treatment-emergent with respect to a given Part/Period if the adverse event occurred after administration of the first dose of study drug in that Part/Period and, if the patient continues onto a subsequent period part, prior to the first dose of study drug in the subsequent Part/Period. Adverse events will be limited to those collected within this protocol (ie, for rollover patients, AEs collected under the protocol of the rollover study but not in this study will not be in this

Concert Pharmaceuticals, Inc.  
Statistical Analysis Plan – CP543.2004

study). The number and percentage of patients who report TEAEs will be summarized by treatment group, system organ class, and preferred term.

Treatment emergent adverse events will also be summarized by intensity as well as relationship to study drug.

Partial dates will be imputed for the purposes of defining TEAEs as follows:

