Patients who report the same preferred term on multiple occasions will be counted once per Part/Period for the preferred term: under the highest severity when summarized by severity and under the closest relationship to study drug when summarized by relationship. Missing severity or relationship will not be imputed. If a patient reports multiple preferred terms for a system organ class, the patient will be counted only once for that system organ class.

Concert Pharmaceuticals, Inc.  
Statistical Analysis Plan – CP543.2004

The number and percentage of patients who experience TEAEs will be summarized by treatment group and overall for each Part/Period for the following:

- By system organ class and preferred term
- By severity/intensity, system organ class, and preferred term
- By relationship to study drug, system organ class, and preferred term
- Serious adverse events by system organ class and preferred term
- Serious adverse events by relationship to study drug, system organ class, and preferred term
- Adverse events resulting in discontinuation of study drug by system organ class and preferred term
- Adverse events that result in study drug dose interruption by system organ class and preferred term

The number of TEAEs (events) will also be reported. By-patient listings will include all adverse events. TEAEs will be flagged.

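### Part A Period 2 TEAEs are tabulated without allowing for time at risk, so arms that reach LOM sooner show lower crude percentages at equal true risk

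*SAP*

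**What the plan says.** Length of Period 2. SAP Section 3 (Part A, Period 2) states: "Patients in Part A, Period 2 will stay on their assigned dose for a maximum of 24 weeks or until they meet the criteria". What is meant here is LOM, a SALT score above 20. Section 3 continues: "Any patient meeting the LOM criteria at any assessment timepoint during Part A, Period 2 will enter Part B of the study".

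TEAE window. Under SAP Section 9.3, an event belongs to a given Part or Period if it starts after the first dose there and, for a patient who continues, "prior to the first dose of study drug in the subsequent Part/Period". For a patient with LOM, Period 2 counting therefore stops at Part B Day 1.

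Summary measure. SAP Section 9.3: "The number and percentage of patients who experience TEAEs will be summarized by treatment group and overall for each Part/Period". Under SAP Section 4 the default denominator is the number of patients in the column header. Section 9.3 adds: "The number of TEAEs (events) will also be reported". No person-time denominator is given for either measure.

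Exposure. SAP Section 9.2: "Study drug exposure will be summarized for each treatment group and overall for each Part/Period". It is not linked to the adverse event tables.

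Unequal follow-up. SAP Section 8.2.1 recognises it for the SALT endpoint: "Due to the variable time on study for each patient within Part A Period 2". There it leads to an end-of-period analysis visit. Section 9.3 has no counterpart.

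Outputs. SAP Appendix 15.4 lists no exposure-adjusted or time-to-first-event table for adverse events. The Period 2 TEAE tables (14.3.1.1.2 to 14.3.1.10.2) are all marked for the abbreviated report.

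**The concern.** Leaving Period 2 is triggered by the efficacy outcome, so time at risk for adverse events depends on how well an arm holds its regrowth. A patient with LOM at Week 4 contributes about 4 weeks, and a patient who maintains contributes 24. A crude percentage treats the two alike.

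The direction can be predicted once the order of LOM is known. Protocol Section 5.2.1 cites some literature evidence that stopping a JAK inhibitor leads to loss of regrown hair, which points to earlier exit on placebo. The same section reports that 4 mg BID did not differ from placebo for regrowth, so the 8-to-4 mg arm may also leave earlier than the 12-to-8 mg arm. Crude percentages could then suggest a dose gradient between the two reduced-dose arms that is only a difference in follow-up. The Total column in these tables pools the unequal windows.

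At stake is how the Period 2 safety tables in the NDA package are read. With no testing planned, the displayed percentages carry most of the message.

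**Working it through.** **The plan's own figure.** About 50 Responders per dose group, randomised 1:1 (Protocol Sections 8.3 and 13.1): 50 × 1/2 = 25 per arm, which reproduces the stated figure. The documents state no TEAE rate, LOM rate or power calculation.

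**Inputs from the documents.** SALT visits are at Weeks 4, 8, 12, 16, 20 and 24 of Period 2. Exit occurs at the visit where LOM is met. Otherwise follow-up is 24 weeks.

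**Assumptions.** The first-TEAE hazard h is constant and the same in every arm. The LOM probability q is constant per visit, with q = 1 − (1 − C)^(1/6), where C is the cumulative LOM proportion by Week 24.

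**Formulas.**
- Mean weeks at risk = 4 × C / q.
- Crude TEAE percentage = sum over exit times t of P(exit at t) × (1 − exp(−h × t)), including patients who complete 24 weeks.

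**Numbers at h = 0.02 per week.** With full 24-week follow-up, 1 − exp(−0.48) = 38.1% would have a TEAE.

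| LOM by Week 24 | q per visit | Mean weeks | Patient-years per 25 | Crude TEAE % |
|---|---|---|---|---|
| 20% | 0.037 | 21.9 | 10.5 | 35.1 |
| 30% | 0.058 | 20.8 | 10.0 | 33.5 |
| 50% | 0.109 | 18.3 | 8.8 | 29.9 |
| 80% | 0.235 | 13.6 | 6.5 | 22.9 |

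Spurious gap, 30% versus 50% LOM: 33.5 − 29.9 = 3.6 points, about 1 patient in 25. For 20% versus 80%: 35.1 − 22.9 = 12.2 points, about 3 patients in 25.

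**Range over the hazard, 20% versus 80% LOM.**

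| h per week | Crude % at 20% LOM | Crude % at 80% LOM | Gap (points) |
|---|---|---|---|
| 0.005 | 10.3 | 6.5 | 3.8 |
| 0.01 | 19.6 | 12.5 | 7.1 |
| 0.02 | 35.1 | 22.9 | 12.2 |
| 0.04 | 57.3 | 39.2 | 18.1 |
| 0.08 | 80.5 | 59.8 | 20.7 |

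**Noise.** With 25 per arm and proportions near 35% and 25%, the standard error of a difference is √(0.35 × 0.65/25 + 0.25 × 0.75/25) = 0.129, about 13 points. The larger gap is about one standard error.

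**Does adjustment remove the gap?** At a constant hazard, expected weeks at risk to first event equal the crude proportion divided by h: 0.351/0.02 = 17.6 weeks and 0.229/0.02 = 11.5 weeks. Events over that time give 0.02 per week in both arms, about 1.04 per patient-year. A Kaplan-Meier curve censored at Period 2 exit estimates 38.1% at Week 24 in both, if exit is unrelated to adverse event risk.

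**End of the window.** Protocol Section 13.4.5 ends the TEAE window at Week 24 or Early Termination. The SAP sets no end for patients who do not continue. If every patient without LOM also contributed the 4-week safety follow-up, the 20% versus 80% gap at h = 0.02 would be 38.9 − 23.9 = 15.0 points.

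**The case against.** All safety summaries are descriptive, and neither document specifies a between-arm adverse event difference or test. Period 2 exists to study durability of regrowth. That stands: a reader might infer that a formal reduced-dose versus placebo safety contrast goes into the NDA, but only side-by-side tables do.

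The time at risk is not hidden. The same abbreviated report carries exposure by arm (Table 14.1.7.2), Kaplan-Meier time to first LOM (Table 14.2.4.1) and Kaplan-Meier time to treatment discontinuation (Figure 14.1.2.2), and event counts are reported. A reader can see the imbalance and form a rough event rate. This stands in part: the summary tables do not give time to first event, so a first-event rate cannot be rebuilt from them.

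A reader might set a whole arm followed for 8 or 12 weeks against one followed for 24. At a hazard giving 40% over 24 weeks, that shows 15.7% or 22.5% against 40%. The documents do not support this as the expected size. Exit is visit by visit, and even 80% LOM leaves a mean of 13.6 weeks under the model above, while the full-24-week comparator would need almost no LOM.

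The expectation of earlier exit on placebo is thin. Protocol Section 5.2.1 says there are no data on stopping CTP-543, and if 4 mg holds regrowth no better than placebo, the two arms from the 8 mg group may differ little. If placebo does leave sooner, the distortion works against the reduced doses and does not flatter the product against placebo. Both points stand. They limit the size and consequence but do not remove the mechanism.

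Finally, rates are fragile in arms this small. One serious event in 6.5 patient-years is 1/6.5 × 100 = 15 per 100 patient-years, with an exact 95% interval of about 0.4 to 86. That stands and narrows the remedy.

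**Conclusion.** The concern holds as a fault of presentation in the Period 2 TEAE tables. With equal true risk, arms that reach LOM sooner show lower crude percentages, and nothing in SAP Section 9.3 or Appendix 15.4 adjusts for it. The mechanism and its direction follow from the exit rule and the TEAE window.

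The size does not follow from the documents. It rests on an assumed constant hazard, assumed LOM proportions and exit unrelated to adverse event risk. It is small when LOM proportions are similar and can match the sampling noise when they differ widely. Which arms are affected depends on the order of LOM, for which the protocol gives only a qualitative hint. A claim that the plan makes a biased safety comparison in favour of the product, or that the gap will be large, is not supported.

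The change is worth making because it removes a predictable distortion at little cost. It has no bearing on sample size or patient care.

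**What to change.** For the Part A Period 2 adverse event tables in SAP Section 9.3 and Appendix 15.4:

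- Keep the crude percentages and event counts, and show patient-years (or median time) at risk by arm in the column headers.
- For overall TEAEs, add an exposure-adjusted incidence rate by arm: patients with a first event per 100 patient-years at risk, with a 95% confidence interval. Time at risk runs to the first event or to the end of the Period 2 window.
- Add a Kaplan-Meier time to first TEAE, censored at Period 2 exit, as a check on the constant-rate assumption. It matters if events cluster soon after the dose change, since the rate would then be inflated in the arm with shorter follow-up.
- For serious events, discontinuations and preferred terms, counts with patient-years at risk suffice. Rate intervals would be uninformative at about 25 patients per arm.
- State when the Period 2 window ends for patients who do not enter Part B, and reconcile this with Protocol Section 13.4.5.

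The cost is some programming, with no new data collection. The rate assumes a constant hazard, and both measures assume that exit is unrelated to adverse event risk. Late Kaplan-Meier estimates may rest on few patients: at 80% LOM only about 25 × 0.20 = 5 per arm complete Period 2 without LOM.

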#### **9.4. Deaths, Serious Adverse Events, and Other Significant Adverse Events**

A serious adverse event is an adverse event that fulfills the following criteria:

- Is fatal (results in death);
- Is life-threatening (Note: the term "life-threatening" refers to an event in which the patient was at risk of death at the time of the event; it does not refer to an event that could hypothetically have caused death had it been more severe);
- Requires inpatient hospitalization or prolongation of existing hospitalization (hospitalization is defined as an inpatient admission, regardless of length of stay);
- Results in persistent or significant disability/incapacity (a substantial disruption of the patient's ability to conduct normal life functions);
- Is a congenital anomaly/birth defect; or
- Constitutes an important medical event that may jeopardize the patient or may require medical or surgical intervention to prevent one of the other outcomes listed above.

Serious adverse events will be summarized according to Section [9.3](#).

By-patient listings will be provided for any deaths, serious adverse events, and adverse events leading to discontinuation of treatment. TEAEs that result in dose interruption will also be identified in these listings.

#### **9.5. Clinical Laboratory Evaluation**

Clinical laboratory samples should be collected at the beginning of each clinic visit and just prior to a dose on all Study Visit Days and will be processed by a central laboratory. In the event a

Concert Pharmaceuticals, Inc.  
Statistical Analysis Plan – CP543.2004

patient is unable to attend an in-clinic visit due to COVID-19, clinical laboratory blood draws may be performed by a Home Health Care agency or a local laboratory.

Clinical laboratory variables will be presented in 4 main ways, for each Part/Period of the study. First, change from baseline to each scheduled visit. Only post-baseline values on treatment (i.e., on the same date or prior to last dose of study drug) will be eligible for change from baseline calculations. Summary statistics for the mean and mean change from Part A Period 1 baseline will be reported for Part A Period 1, Part A Period 2, and Part B. The mean and mean change from Part A Period 2 baseline will be reported for Part A Period 2 and Part B. The mean and mean change from Part B baseline will be reported for Part B

Second, treatment-emergent potentially clinically significant (PCS) laboratory values will be identified. Potentially clinically significant values are defined as those that meet Grade 3 or Grade 4 toxicity criteria from the CTCAE criteria (or Grade 2 or higher for platelets). Laboratory values will be graded using CTCAE version 5.0, for those values included. CTCAE grades will be based solely on numeric results and without regard to other symptoms based on clinical judgment. For laboratory parameters whose CTCAE grading is independent of baseline criteria, treatment-emergent PCS laboratory values are those in which the baseline value is not PCS and the post-baseline value is PCS. For laboratory parameters whose CTCAE grading is dependent upon baseline criteria, any post-baseline grading of Grade 3 or Grade 4 (or Grade 2 or higher for platelets) will be considered treatment-emergent. The number and percentage of patients with treatment-emergent PCS laboratory values will be summarized by treatment group and overall for each clinical laboratory variable patient to CTCAE grading. For this analysis, the visit with the highest CTCAE grade value within a window will be selected.

Third, box plots of hemoglobin, platelets, and neutrophils will also be provided with dose interruption limits included as reference lines (see Protocol Section 10.2.1).

Finally, the count and percentage of abnormal laboratory values per parameter, where applicable, will be provided. Additionally, a listing of patients with Abnormal laboratory values will be provided.

These analyses will be repeated for serum chemistry results, hematology results, and lipid results (where lipid tests include total cholesterol, low-density lipoprotein, high-density lipoprotein, and triglycerides). Laboratory results will also be listed. Reference ranges for each clinical laboratory parameter will also be summarized in a data listing.

Pregnancy test results will be listed only.

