Event	Day -28 to Day -1 (Visit 1)	Randomization ^{1, 2} Day 1 (Visit 2)	Week 2 (Visit 3)	Week 4, 8 (Visit 4, 5)	Week 12 (Visit 6)	Week 16, 20 (Visit 7, 8)	Week 243,4 (Visit 9)	Week 28 ⁵ (Visit 10)	Week 32 (Visit 11)	Week 36 (Visit 12)	Week 40, 44 (Visit 13, 14)	Week 484 (Visit 15)	Safety Follow-Up Visit
Informed consent	X												
Eligibility assessment	X	X											
Demographics	X												
Medical history	X	X											
Randomization		X					X^7						
PE	X	X					X					Х	X
Brief PE				X	X	X			X	X	Х		
Height	X												
Weight	X	X		X	X	X	X		X	X	X	X	X
Pregnancy test ⁸	X	X ⁹		X	X	X	X	X	X	X	X	X	
Tuberculosis test	X												
Clinical laboratory testing ¹⁰ , 11	X ¹²	X	X	X	X	X	X	X	X	X	X	X	X
Lipid assessment ¹³		X			X		X			X		X	X
HBV and HCV test	Х												
12-lead electrocardiogram	Х	X			Х		X			X		Х	X
Vital signs	X	X		X	X	X	X		X	X	Х	X	X
SALT assessment	Х	X		X	X	X	X	X^{14}	X^{14}	X^{14}	X14	Х	
Photographs	X	X		X	X	X	X	X	X	X	Х	X	
SPRO and QPRO		X			X	X	X						
CGI-S and PGI-S		X			Х	X	X						
CGI-I and PGI-I					X	X	X						
Dispense study drug		X		X	X	X	X^7	X^{15}	X^{15}	X^{15}	X15		
Pharmacokinetic blood sampling ¹⁶		X			X		X						
Study drug accountability				X	X	X	X		X	X	X	X	_
Adverse events	X				X					X			X
Concomitant medications	X		X			X				X			

PE = Physical Examination; HBV= hepatitis B virus; HCV = hepatitis C virus; SPRO = Satisfaction of Hair Patient Reported Outcome; QPRO = Quality of Hair Patient Reported Outcome; CGI-S = Clinical Global Impression of Severity; CGI-I = Clinical Global Impression of Improvement; PGI-S= Patient Global Impression of Improvement; PGI-I = Patient Global Impression of Improvement;

- ¹ Day 1 (Visit 2) may occur any time after Screening laboratory results are available and reviewed by the Investigator.
- ² For Part A, Period 1, all subsequent visits and week increments should be based on the date of Visit 2. All visit windows are ± 2 days.
- ³ Week 24 from Part A, Period 1 will also serve as the Day 1 visit for Part A, Period 2 for those who meet criteria to continue into the Dose Modification Phase.
- ⁴ Also serves as the Early Termination Visit for patient withdrawal in this period.
- ⁵ For Part A, Period 2, all subsequent visits and week increments should be based on the date of Week 24 (Visit 9). All visit windows are ±2 days.

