11.10. Clinical Laboratory Assessments

Clinical laboratory assessments are presented in Section 18.1. Clinical laboratory samples should be collected at the beginning of each clinic visit and just prior to a dose on all Study Visit Days and will be processed by a central laboratory. In the event a patient is unable to attend an in-clinic visit due to COVID-19, clinical laboratory blood draws may be performed by a Home Health Care agency or a local laboratory. Patients should try to have laboratory blood draws performed in the morning and dose study drug after clinical laboratory blood draws are completed.

The results of clinical laboratory tests conducted at the Screening Visit (and prior to dosing) must be assessed by the Investigator to determine each patient's eligibility for participation in the study. The Investigator should indicate review of the laboratory reports throughout the study by signing and dating each report.

All clinical laboratory results that fall outside the reference range will be interpreted by the Investigator as Abnormal, not clinically significant, or Abnormal, clinically significant. Laboratory results deemed Abnormal, clinically significant will be recorded as an adverse event in the eCRF (see additional criteria outlined in Section 12.1). Clinically significant laboratory abnormalities indicative of hematologic or other effects requiring intervention should be discussed with the Medical Monitor(s). Additional tests and evaluations required to establish the significance or etiology of a clinically significant abnormal result or to monitor the course of an adverse event should be obtained when clinically indicated. Whenever possible, the etiology of the clinically significant abnormal findings will be documented on the eCRF.

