original collected data. The mean and median will be reported to an additional level of precision than the original observations, and the standard deviation will be reported to two additional levels of precision than the original observations. The precision for some original collected data and derived variables are longer than required for clinical interpretation (eg, >15 decimals). In these situations, the number of decimal places will be determined by the table of precision included as an attachment.

All efficacy summaries are descriptive with no statistical hypothesis testing. Confidence intervals and estimated treatment differences will be rounded to one additional decimal place from the original data, or a maximum of two decimal places. Standard error will be reported to an additional level of precision. Results which cannot be determined will be displayed as “NA”, “NE”, or similar.

Treatment start date for each part and period will be defined as the date of randomization or re-randomization for the respective part or period. If the treatment start date for Part A Period 2 is equal to the treatment end date for Part A Period 1 as collected on the eCRF, it will be assumed that the treatment day is associated with Part A Period 2. One day will be subtracted from the treatment end date for Part A Period 1. Similarly, if the treatment start date for Part B is equal to the treatment end date for Part A Period 2, it will be assumed that the treatment day is associated with Part B. One day will be subtracted from the treatment end date for Part A Period 2.

Date of last dose is collected on the *Treatment Discontinuation/Completion* eCRF page for each part/period. For patients with missing or partial date of last dose, or for patients who are ongoing at the time of the NDA submission, the date of last dose (ie, treatment end date) will be imputed. Date of last dose will be imputed as follows:

- For entirely missing dates for patients who are not ongoing or for partial dates where the month and day are missing, date of last dose will be imputed as the last visit date that is not a follow-up visit within a period or part.
- For partial dates where only the day is missing, the day will be imputed as the last day of the month. If this imputed date is after the treatment start date of the next part or period, or the study discontinuation date of that part or period, the day will be imputed to one day before the treatment start date of the next part or period.

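### SAP 9.5 does not say which last dose defines an on-treatment lab value, so inclusion in the changeover-visit mean-change results can depend on hair response

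*SAP*

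**What the plan says.** **The eligibility rule.** SAP 9.5 states: "Clinical laboratory variables will be presented in 4 main ways, for each Part/Period of the study". The first of the four is change from baseline, and for that calculation alone it adds: "Only post-baseline values on treatment (i.e., on the same date or prior to last dose of study drug) will be eligible". It names no Part or Period for the last dose and makes no exception for a visit that closes one period and opens the next.

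**The last-dose date.** SAP 4 collects the date of last dose separately for each part/period and treats it as the same thing as the treatment end date: "the date of last dose (ie, treatment end date) will be imputed". Each period starts on its (re-)randomization date. Where two periods meet, the SAP sets a condition, "If the treatment start date for Part A Period 2 is equal to the treatment end date for Part A Period 1", assigns the shared day to Period 2, and then says: "One day will be subtracted from the treatment end date for Part A Period 1". The parallel rule for entry to Part B is: "One day will be subtracted from the treatment end date for Part A Period 2". SAP 7.3 also uses the last-dose date per Part/Period, to compute time on treatment.

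**The visits.** Protocol Table 1, footnote 3, says: "Week 24 from Part A, Period 1 will also serve as the Day 1 visit for Part A, Period 2", for patients who continue. Footnote 7 has re-randomization and dispensing at Week 24 for those patients only. Table 2, footnote 2, puts Part B Day 1 on the same day as the last Period 2 visit. On timing of blood draws, Protocol 11.10 says: "Clinical laboratory samples should be collected at the beginning of each clinic visit and just prior to a dose on all Study Visit Days".

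**The concern.** The Week 24 sample is the laboratory value at the longest Period 1 exposure to each dose. The LOM-visit sample is the last one on the reduced dose or placebo. Both are drawn before the next period's first tablet, so clinically they belong to the period that is ending. If the eligibility rule removes them from that period, it does so according to efficacy status, because only responders continue at Week 24 and only patients with LOM enter Part B.

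The Week 24 mean change for 8 mg against 12 mg would then be selected on response. In Period 2, an arm that loses hair faster would lose more laboratory change values. The Part A change tables for hematology, chemistry and lipids (in Period 1, Tables 14.3.4.1.1, 14.3.4.2.1 and 14.3.4.3.1) are all marked for the abbreviated report that supports the NDA. The Part B tables, where the LOM-visit value would serve as baseline, are not.

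**Working it through.** **Date check.** Let D be the changeover visit date, which is also the start of the next period. Let L be the lab date, E the recorded last-dose date of the ending period, and E* the date after SAP 4's adjustment: E* = E − 1 if E = D, otherwise E* = E. Under the period-specific reading a value is eligible if L ≤ E*. Under the study-wide reading it is eligible if L is no later than the patient's last dose anywhere in the study.

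| Patient and dates | Period-specific | Study-wide |
|---|---|---|
| Continues; L = D, E = D | E* = D − 1: excluded (kept without the subtraction) | kept |
| Continues; L = D, E = D − 1 | E* = D − 1: excluded by 9.5 alone | kept |
| Continues; L = D − 1, E = D | E* = D − 1: kept | kept |
| Continues; L = D, E recorded after D | kept | kept |
| Does not continue; L = D, tablet taken on D | kept | kept |
| Does not continue; L = D, last tablet on D − 1 | excluded | excluded |

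The first two rows are the expected pattern for a continuing patient. The subtraction causes the exclusion only in the first; in the second, the on-treatment rule is enough. The last row applies under both readings, because a patient who leaves after Period 1 has only one last dose.

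**Size at Week 24.** Inputs are about 170 patients on 8 mg and 130 on 12 mg (Protocol 13.1), about 50 responders per dose group, and 1:1 re-randomization (Protocol 8.3, SAP 7.2). The plan's own figures reproduce: 170 + 130 = 300; 50/2 = 25 per Period 2 arm; 4 × 25 = 100 in Period 2.

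Under the period-specific reading, the share with no Week 24 change value is:

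- 8 mg: 50/170 = 29.4%, leaving at most 170 − 50 = 120
- 12 mg: 50/130 = 38.5%, leaving at most 130 − 50 = 80
- overall: 100/300 = 33.3%

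Those left are essentially non-responders, fewer still if some took their last tablet the evening before.

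By Table 1, hematology and chemistry have a Week 20 sample to fall back on. Lipids are scheduled post-baseline in Period 1 only at Weeks 12 and 24, so a continuing responder would keep one scheduled lipid change value. (The text of Protocol 8.1 says lipids are assessed every 4 weeks; Table 1 does not show that.)

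**Size at the LOM visit.** The documents give no LOM rate, so the loss lies anywhere from 0 to about 25 patients per arm. A patient whose LOM is found at Week 28, the first Period 2 visit, would have no scheduled post-baseline change value in the Period 2 tables.

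**Check of the remedy.** With L ≤ E + 1 and E unadjusted, E = D gives D ≤ D + 1 and E = D − 1 gives D ≤ D. Both are kept, for continuing and non-continuing patients alike. The Week 24 rows return to as many as 170 and 130 patients before dropout and missed draws. The next scheduled sample is nominally at least two weeks later, so the extra day should admit no off-treatment scheduled value.

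**The case against.** The best defence is that SAP 9.5 speaks of the last dose of study drug with no Part or Period attached, while SAP 9.3 says so explicitly when it means dosing within a Part/Period. Read study-wide, the rule has a sensible purpose: it removes off-drug samples such as the Safety Follow-Up draw, and no patient who goes on dosing loses a changeover value. The subtraction in SAP 4 is conditional, its stated role is to assign a shared treatment day to one period, and 9.5 does not refer to the adjusted date. Allowing samples on the day of the last dose suggests that the authors meant to keep same-day samples.

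Much of this stands. The text is ambiguous, and the subtraction is not always the cause. The rule covers only the change calculation: it is not stated for visit means, potentially clinically significant values, box plots, abnormal counts or listings, and the changeover value still serves as the next period's baseline. These are descriptive safety summaries.

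What does not stand is that the study-wide reading cures the problem. Non-responders receive no study drug at Week 24, and blood is drawn before any dose that day. If the last tablet was the evening before, their Week 24 change value is dropped while responders' values are kept. The selection then runs the other way.

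A reader might go further and infer that the SAP certainly deletes every responder's Week 24 labs, that the Week 24 table rows hold non-responders only, or that 29% and 38% are minimum losses that could approach 100%. The documents do not support this. The loss among continuing patients is zero under the study-wide reading. Samples dated before the changeover day, and patients with LOM who do not start Part B that day, can be kept. The visit means are not restricted. The documents do not show how many non-responders skip a tablet on the visit day.

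**Conclusion.** The concern holds as a rule whose unclear wording can make inclusion in laboratory mean-change results depend on response, whichever way it is read. Under the period-specific reading, which SAP 4, SAP 7.3 and the per-Part/Period layout of 9.5 favour, the Week 24 mean change omits essentially all continuing responders: about 29% of the 8 mg group and 38% of the 12 mg group. The Period 2 mean change omits the LOM-visit value, by an amount that cannot be sized. Under the study-wide reading, the loss falls on non-responders who took their last tablet the evening before.

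The percentages assume the planned arm sizes, about 50 responders per group who all continue, and samples drawn on the changeover date. Severity is moderate: one of four laboratory presentations is affected, although it goes into the abbreviated NDA report. The SALT primary endpoints are unaffected.

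**What to change.** In SAP 9.5, define an on-treatment value as one dated on or before the date of last dose in that Part/Period plus 1 day, using the last-dose date before SAP 4's one-day subtraction. Add that a pre-dose sample at a changeover visit (Week 24 or the LOM visit) counts both as the final on-treatment value of the ending Part/Period and as the baseline of the next. The extra day is needed as well as the changeover statement, because the latter alone would not protect the final samples of patients who do not continue.

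The cost is a sentence or two in the SAP and a small programming change before the tables are run. No new data are needed.
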